6.2 Clinical Adverse Events

6.2.1 Treatment-emergent AEs (TEAEs)

All AEs will be analyzed based on the principle of treatment emergence. A treatment-emergent AE is defined as an AE that started or worsened after the start of first dose of study treatment.

To define treatment emergence for AEs with missing start or stop date or time the following additional criteria will be used:

- if both the start and stop dates for a particular AE are missing, then that AE is considered treatment emergent;
- if the start date for a particular AE is missing and the stop date/time falls after the first dose date/time, then that AE is considered treatment emergent;
- if the start date for a particular AE was the same as the first dose date, and the start time was missing, then that event is considered treatment emergent.

For AEs with a partial start date, the year/month of the event date will be compared to that of the first dosing date to determine whether the event is treatment emergent.

In addition, SAEs that occurred since a subject was screened in the study and prior to the first dose of study treatment, which by definition are not treatment-emergent, will be included in relevant listings but will not be summarized.

Only TEAEs will be included in the AE tables, unless otherwise specified.

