17.4.2. Safety Analyses

Safety analyses will be performed by as-treated treatment group for treated participants. Safety endpoints include the frequency and proportion of participants with AEs, SAEs, AEs leading to discontinuations and deaths, and other significant AEs reported on case report forms. Other safety endpoints include laboratory abnormalities, changes in laboratory parameters, changes in vital signs, physical findings, and ECGs.

In general, AE presentations will be by system organ class and preferred term.

The primary safety analyses will be for comparative safety of BIIB092 to placebo in the double-blind treatment period. Safety endpoints will include data up to the start of the open-label extension period for participants who completed the double-blind treatment period and continue into the open-label extension, or up to last dosing date plus 30 days for participants discontinuing study treatment during the double-blind treatment period.

Additional safety analyses will include all events reported through the time of database lock for the cumulative BIIB092-treated participants. Safety endpoints will include data from the first dose of BIIB092 in the study up to the last dose of BIIB092 treatment in the study plus 30 days.

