1.4 Treatment

Study treatment is defined as any investigational treatment(s), marketed product(s), placebo or medical device intended to be administered to a study participant according to the study randomization or treatment allocation

| Study Treatment | Unit dose strength(s)/Dosage level(s) | Dosage formulation Frequency of Administration | Route of Administration |
|------------------------|---|---|--------------------------------|
| BIIB092 | 2000 mg | Once every 4 weeks (Q4W) | IV |
| Placebo | Matching dose volume 0.9% NaCl or 5% Dextrose | Once every 4 weeks (Q4W) | IV |

All participants are centrally randomized using an Interactive Response Technology (IRT). Before the study is initiated, each user receives log in information and directions on how to access the IRT. Randomization is stratified by country and screening CTT Part 2 completion time of either ≤ 170 or > 170 seconds.

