3.2 Population

- Dosed subjects: enrolled subjects who received at least one dose of study therapy, i.e., blinded therapy (BIIB092 or placebo) or open-label BIIB092. This is the same as the “Treated participants” in Section 17.2 of the protocol.
- Intent-to-treat (ITT) population:
The intent-to-treat population is defined as all randomized subjects who received at least one dose of blinded study treatment (BIIB092 or placebo).
- Safety population: all randomized subjects who received at least one dose of study treatment (BIIB092 or placebo).
- Efficacy MRI population: the subset of the ITT population who had a least one measurable brain volumetric measurement.
- Safety MRI population: the subset of the safety population who had a least one post-baseline safety MRI.
- Serum PK analysis population: the subset of the safety population who had at least one measurable post-baseline BIIB092 concentration in serum.

- CSF PK analysis population: the subset of the safety population who had at least one measurable post-baseline BIIB092 concentration in CSF.
- CSF PD analysis population: the subset of the safety population who had both baseline and at least one measurable post-baseline N -terminal tau CSF sample.
- Anti-drug antibody (ADA) analysis population: the subset of the safety population who had at least one post-dose sample evaluable for ADA.

OLE treatment groups for analyses

Analyses for efficacy data will be displayed by the following treatment groups according to randomization assignment at the start of the placebo-controlled period:

- BIIB092 early start: subjects who are assigned to (1) receive BIIB092 in the placebo-controlled period and (2) continue receiving BIIB092 in the OLE period
- BIIB092 late start: subjects who are assigned to (1) receive placebo in the placebo-controlled period and (2) switch to BIIB092 in the OLE period

Unless otherwise specified, analyses for safety, PK, and ADA data will be displayed by the following treatment groups according to dose received:

- BIIB092 early start: subjects who receive BIIB092 in the placebo-controlled period (regardless of randomization assignment)
- BIIB092 late start: subjects who receive only placebo in the placebo-controlled period (regardless of randomization assignment) and switch to receive BIIB092 in the OLE period
- BIIB092 total: subjects in either BIIB092 early or late start treatment groups

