3.2 Analysis Period

Depending on the purpose, different analyses will be conducted on the following study periods:

1. **OLE period**. Only data in the OLE period will be included in these analyses. This OLE analysis period will be applied to all the AE analyses, and the analyses will include all subjects who were dosed in the OLE period.
2. **Placebo-controlled and OLE period**. All the data in the placebo-controlled and OLE periods will be included in these analyses. This analysis period will be applied to all efficacy analyses. The analyses will include all subjects who were dosed in the study including those who did not enroll into the OLE period.
3. **Active treatment (placebo-controlled and OLE) period**. The active treatment period is defined as the study period(s) in which a subject received BIIB092. For early start subjects, all data from placebo-controlled and OLE periods will be included. For late start subjects,

only data in the OLE period will be included. This analysis period will be applied to all safety analyses, and the analyses will include all subjects who were dosed in the study except for subjects who received only placebo in the placebo-controlled period and did not get dosed in the OLE period.

For a given output, both the analysis population and the analysis period will determine which subjects will be included. For example, the incidence table of adverse events in the OLE period will include subjects in the safety population for the OLE period, i.e., all randomized subjects who received at least one dose of study treatment in the OLE period. The incidence rate table of adverse events in the active treatment (placebo-controlled and OLE) period will include subjects in the safety population for the active treatment period, i.e., all randomized subjects who received at least one dose of treatment in the active treatment period. In this SAP we do not separately define the analysis population in each analysis period.

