6.1.4 Incidence, incidence proportion and incidence rate

- Incidence and incidence proportion will be provided in incidence proportion tables. Incidence is defined as the number of subjects who experienced an event. Incidence proportion is defined as the number of subjects who experienced an event divided by total number of subjects in the analysis population, i.e., percentage. Each subject will be counted only once within each category.

- Incidence and incidence rate will be provided in incidence rate tables. Two different kinds of incidence rate tables will be provided as appropriate for different analyses. Definitions are provided below.
 - Follow-up adjusted incidence rate (FAIR) – defined as the number of subjects with an event divided by the total follow-up time among the subjects in the analysis population (e.g., incidence rate per 100 subject-years). The total follow-up time (subject-years) is the sum of all subjects' follow-up time, where a subject's follow-up time is calculated as the number of days (inclusive) from first dose of treatment until the last day on study divided by 365.25. For active treatment period analyses, the first dose of treatment is considered the first dose received in the study period (PC or OLE) in which a subject first receives BIIB092. Each subject will be counted only once within each category.
 - Exposure-adjusted incidence rate (EAIR) – defined as the number of subjects with an event divided by the total exposure adjusted follow-up time (i.e. total time at risk for the event) among the subjects in the analysis population (e.g., incidence rate per 100 subject-years). The exposure adjusted follow-up time (time at risk for the event) for a subject is the time from the first dose of study drug in the first BIIB092 dosing period (PC or OLE) to the initial occurrence of the event for subjects who experienced the event, and is the time from first dose of study drug in the first BIIB092 dosing period to the end of follow-up (the last day on study) for subjects who did not experience the event. The total time at risk is the sum of all subjects' time at risk. Each subject will be counted only once within each category.

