6.4.1 Analysis of Central Tendency

Summary statistics (n, mean, SD, median, minimum, and maximum) will be presented for each ECG parameter and the corresponding changes from baseline by the OLE treatment group through the combined placebo-controlled and OLE period. Frequency distribution of maximum postdose ECG intervals tables will also be generated.

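### The OLE SAP does not tie treatment emergence or post-dose ECG maxima to the first BIIB092 period, so late-start AEs with unclear or carried-over onset, and placebo-period ECGs, can be misattributed

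*SAP*

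**What the plan says.** **Adverse events.** OLE SAP 6.2.1 reads: "A treatment-emergent AE is defined as an AE that started or worsened after the start of first dose of study treatment". Section 1.4 makes clear that this includes placebo: "Study treatment is defined as any investigational treatment(s), marketed product(s), placebo or medical device intended to be administered to a study participant". The late-start safety group (Section 3.2, Population) is "subjects who receive only placebo in the placebo-controlled period (regardless of randomization assignment) and switch to receive BIIB092 in the OLE period". The date rules in 6.2.1 refer to the same first dose. An AE with both dates missing is emergent. An AE with a missing start is emergent if it stops after the first dose. A partial start date is compared by year and month with the first dosing date.

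**Time origins used elsewhere.** For rates in the active treatment period, 6.1.4 says "the first dose of treatment is considered the first dose received in the study period (PC or OLE) in which a subject first receives BIIB092". Section 3.3 sets the active treatment baseline in the same way. Protocol 17.4.2, on cumulative BIIB092 exposure, says "Safety endpoints will include data from the first dose of BIIB092 in the study up to the last dose of BIIB092 treatment".

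**Analysis periods.** Section 3.2 (Analysis Period) defines three. For the OLE period, "Only data in the OLE period will be included in these analyses". The active treatment period also holds only OLE data for late-start subjects. The third, the placebo-controlled and OLE period, holds all data and is assigned to efficacy. Section 6.1.2 puts AE analyses on the OLE period and all safety analyses on the active treatment period.

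**ECG.** Section 6.4 uses the active treatment period and its baseline, and Table 11 starts late-start windows at the first OLE dose. Section 6.4.1, however, presents each parameter and "the corresponding changes from baseline by the OLE treatment group through the combined placebo-controlled and OLE period", and adds tables of maximum post-dose intervals. Section 6.4.2 tabulates maximum post-dose QTcF, PR, QRS and change in QTcF, and names neither a period nor the dose from which post-dose is counted.

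**The concern.** For a late-start subject the first dose of study treatment is a placebo infusion about a year before any BIIB092. The emergence rule would suit the placebo-controlled SAP, whose 6.2.1 is worded almost identically. In the OLE SAP, the baseline, the person-time and the late-start visit windows were all moved to the first BIIB092 dosing period, but the emergence rule was not. When the onset of an AE is unclear, or when an AE straddles the switch, the rule cannot separate placebo time from BIIB092 time.

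The ECG wording raises a similar problem. If 6.4.1 is followed as written, values recorded on placebo can enter a column labelled BIIB092, and their changes are measured from a baseline taken at or after them.

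At stake is the early-start versus late-start safety comparison, together with the pooled BIIB092 column. The protocol synopsis makes long-term safety the extension's primary objective, although the endpoint tables label the same endpoint tertiary.

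**Working it through.** No sample size, power or alpha figure in the plan depends on this point, so there is no stated figure to reproduce. On the plan's own assumptions, the placebo arm yields 153 × (1 − 0.25) = 114.75, or about 115, Week 52 completers. That is roughly the most that could become late-start subjects.

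**A. Adverse events in a late-start subject: what the filters decide**

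| AE | 6.2.1 test (from Week 0) | OLE-data filter (3.2, 6.1.2) | Result |
|---|---|---|---|
| Start and stop dated to the placebo period | Emergent | Excluded | Correct |
| Start dated after the first OLE dose | Emergent | Included | Correct |
| Both dates missing | Emergent | No rule assigns it to a period | Undetermined |
| Start missing, stops in the OLE | Emergent | No rule | Undetermined |
| Partial start that cannot be placed before or after the switch | Emergent whenever later than the Week 0 month | No rule | Undetermined |
| Began on placebo, ongoing or worse in the OLE | Emergent by its start alone | Not stated whether onset or presence decides | Wrong either way (below) |

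The last row has two readings. If onset decides, an AE that worsens on BIIB092 is lost. If presence in the OLE decides, an AE that is merely ongoing counts as emergent, because it began after Week 0. An early-start subject whose AE was present before the first BIIB092 dose counts if, and only if, it worsens afterwards. Under both readings the two groups' numerators follow different rules.

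Moving the anchor does not settle every row. An AE with both dates missing is emergent under any anchor, so a period-assignment rule is needed as well.

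**B. ECG**

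Schedule: Weeks 24 and 52 in the double-blind period (Protocol Table 2), then Weeks 76, 100 and every 24 weeks (Protocol Table 3). OLE SAP 5.3 says that too few patients will have reached Week 100 at the interim. Many late-start subjects will therefore have at most one scheduled ECG on BIIB092, at Week 76.

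*By-visit summaries.* With a first OLE dose on Day 365, the placebo Week 24 ECG (Day 169) falls at 169 − 365 = −196. Table 11 windows begin at Day 1 post-dose, so it has no late-start window. The Week 52 ECG is ordinarily the OLE baseline. These summaries are protected.

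*Maximum post-dose tables.* They have no window. If post-dose means after the first dose of any study treatment, the candidates are Week 24 (placebo), Week 52 (placebo) and Week 76 (BIIB092), so 2 of 3 values are not on BIIB092.

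*Illustration.* Assume that each ECG exceeds a limit with probability 0.10, independently. The share of subjects whose maximum exceeds the limit is 1 − 0.9^k:

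- k = 1 (Week 76 only): 1 − 0.9 = 10%
- k = 2 (Week 52 set aside as baseline): 1 − 0.81 = 19%
- k = 3: 1 − 0.729 = 27.1%

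Positive correlation within a subject lowers the last two. For change in QTcF, a Week 52 value that is itself the baseline contributes exactly zero. It cannot move a subject out of the lowest category (30 msec or less), so only the Week 24 value can do so.

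**The case against.** The strongest reply is that Sections 3.2 and 6.1.2 already do the work. Late-start safety data are confined to the OLE, and person-time starts in the same dosing period, so for dated events numerator and denominator agree. This stands. A reader might infer from 6.2.1 alone that a year of placebo-time AEs is reported as BIIB092. If the filter did not exist, that would be a large error. With a constant hazard of 0.2 per year, 1 year on placebo and 1 year of OLE (all assumed), the late-start proportion would rise from 1 − exp(−0.2) = 18.1% to 1 − exp(−0.4) = 33.0%. Because the filter does exist, this inflation does not arise for events with a known onset, and the documents do not support that reading.

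It can also be said that the first dose in 6.2.1 should be read as 6.1.4 reads it. However, 6.1.4 makes that definition within its rate formula, and 6.2.1 does not refer to it. Protocol Appendix 3 counts worsening of a pre-existing condition as an AE, so some carried-over events may be recorded afresh with an OLE start. That shrinks the group but does not settle the rule.

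On ECG, 6.4 and Table 11 are correct, and 6.1.2 could be read as governing 6.4.2, which names no period. This too stands for the by-visit summaries. But 6.4.1 names a different period, one that 3.2 defines as all data. Section 6.4 also calls for all available double-blind and open-label values, and nothing ties post-dose to BIIB092. The maximum tables remain open.

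**Conclusion.** The concern holds in a limited form.

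- **AEs.** The emergence anchor is out of step with the rest of the OLE SAP. The consequence is confined to undated or partly dated AEs and to AEs that began on placebo and are ongoing or worsen in the OLE. The documents give no counts; the number is probably small, and no route to miscounting deaths was found. The direction is not fixed, because events may be wrongly added or wrongly lost.
- **ECG.** Section 6.4.1 conflicts with 6.1.2 and 6.4. By-visit late-start summaries are safe. The unwindowed maximum post-dose tables in 6.4.1 and 6.4.2 can take placebo-period values into the late-start BIIB092 column. The 27% is an illustrative upper bound only. It rests on an assumed 10% rate, independence between ECGs, and counting the Week 52 ECG, which is ordinarily the OLE baseline, as a post-dose value.

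This should be corrected before the OLE tables are programmed, because two programmers could follow the text and produce different tables.

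**What to change.** 1. **OLE SAP 6.2.1.** For active treatment tables, define emergence from the first dose in the dosing period (PC or OLE) in which BIIB092 is first received. For OLE tables, define it from the first OLE dose. Apply the same anchor to every missing- and partial-date rule. Count an AE present before that dose only if it worsens after it. Add a rule that assigns undated and partly dated AEs to the PC or the OLE period.
2. **OLE SAP 6.4.1.** Replace the period named there with the *active treatment (placebo-controlled and OLE) period*.
3. **OLE SAP 6.4.2.** Insert that period, since none is named now. In both 6.4.1 and 6.4.2, define post-dose from the same dose as in item 1.

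Two small repairs could go in at the same time. The vital-sign line plots in 6.5 carry the same combined-period wording. The ECG reference in 6.4 to Table 8 points to the late-start laboratory windows, whereas the ECG windows are Tables 10 and 11.

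Cost: SAP wording and one derivation variable. No new data are needed.

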6.2.2 Summary and incidence analysis

Overall summary of AE table will be done for the OLE period, as well as for the active treatment (placebo-controlled and OLE) period presented by OLE treatment group. The following information will be summarized: the number of subjects with any AE, with any AE by maximum severity (as assessed by the investigator), the number of subjects with any related AE (related to study drug as assessed by investigator), the number of subjects with SAE, the number of subjects with related SAE, the number of subjects with AE leading to study drug discontinuation, the number of subjects with an AE that led to withdrawal from the study and the number of subjects with a fatal event.

The sorting order for AE incidence tables, unless otherwise specified, will be by decreasing frequency order of “BIIB092 total” column within each category in the tables presented by OLE treatment group. A subject is counted only once within each category in each table. For example, for the table of AEs by system organ class and preferred terms sorted by decreasing frequency presented by treatment group, system organ class will be presented in decreasing frequency order of BIIB092 total column, and within each system organ class, preferred terms will be presented in decreasing frequency order of BIIB092 total column. A subject is counted only once within each system organ class and preferred term.

The following AE incidence proportion tables will be provided for the OLE period (presented by the OLE treatment group unless otherwise specified):

1. AEs by system organ class and preferred term sorted by decreasing frequency
2. AEs by system organ class and preferred term sorted by alphabetical order
3. AEs by system organ class, high level group term and preferred term
4. AEs by system organ class
5. AEs by preferred term
6. AEs with an incidence of 2% or more in any treatment group by preferred term
7. AEs with an incidence of 5% or more in any treatment group by preferred term
8. Severe or very severe AEs by system organ class and preferred term
9. Severe or very severe AEs by preferred term
10. AEs by maximum severity by system organ class and preferred term. (System organ class will be presented alphabetically. Preferred terms will be presented in decreasing frequency order. Maximum severity will be presented within each preferred term in the order of mild, moderate, severe, very severe, unknown and total. A subject will be counted only once at the maximum severity within each system organ class and preferred term.)
11. AEs by maximum severity by preferred term. (Preferred terms will be presented in decreasing frequency order. Maximum severity will be presented within each preferred term in the order of mild, moderate, severe, very severe, unknown and total. A subject will be counted only once at the maximum severity within each preferred term.)
12. Related AEs by system organ class and preferred term
13. SAEs by system organ class and preferred term
14. SAEs by preferred term

15. Related SAEs by system organ class and preferred term
16. AEs that led to discontinuation of study treatment by system organ class and preferred term
17. AEs that led to withdrawal from study by system organ class and preferred term
18. SAEs with fatal outcome by system organ class and preferred term
19. AEs by 12-week intervals by system organ class and preferred term
20. SAEs by 12-week intervals by system organ class and preferred term

In addition to listings provided as part of the analysis described in the placebo-controlled SAP, a listing of AEs that led to withdrawal from study will be provided.

